5.2 Anticipated Duration of the Clinical Investigation

We anticipate the entire duration of the investigation to be 24 months.

Dates	Goal	Responsible party(ies)
Month 1-2	Application for FDA approval , response to stipulations, and approval by University of Minnesota	[name], [name], [name]
Month 3-18	Recruitment and screening of subjects	[name], [name], [name]
Months 3-18	Performing the experiments, laboratory analysis of plasma hormone and naloxone concentrations.	[name], [name], [name], [name]
Month12-24	Preparation of manuscript and abstracts for presentation to national medical societies and for publication in peer reviewed journals	[name], [name], [name]

5.3 Evaluation Criteria

5.3.1 Primary Clinical Endpoint

Primary endpoint will be the within person difference in peak epinephrine secretion during the morning episodes of hypoglycemia on days one and two; we will compare this difference between the two treatment conditions (parts 1 and 2). Epinephrine secretion during hypoglycemia is assessed by collecting blood samples for measurement of epinephrine concentrations at baseline and every 15 minutes during the period of hypoglycemia (starting at point where blood glucose is first < 55 mg/dl) in the clamp studies done in the mornings of days 1 and 2 of both parts 1 and 2.

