Version #	Version Date	Significant Changes from Previous Version
01	02/03/2016	Original Protocol Version
02	04/25/2016	Added additional justification for sample size
03	06/28/2016	Change randomization for the first 3 subjects to naloxone
04	01/05/2017	Add 8mg dose of naloxone; change randomization for the first 8 subjects to naloxone
05	01/31/2019	Update study location

Table of Contents

List of Abbreviations	.6
1.0 Study Contact Information	.7
2.0 Introduction / Background and Rationale	.8

Study Summary

Title	Intra-nasal Naloxone for treatment of impaired awareness of hypoglycemia
Short Title	Intra-nasal Naloxone for impaired awareness of hypoglycemia
IRB Number	1603M84961
Study Sponsor	[name]
Phase	1
Principal Investigator	[name]
Study Design	Single center, single-blind, randomized, cross-over
Study Duration	24 months
Study Center(s)	Clinical Research Unit (CRU)
Objectives	Primary Objective: To evaluate intra-nasal Naloxone as a therapy for prevention and treatment of impaired awareness of hypoglycemia.
	Secondary Objective: Characterize naloxone pharmacokinetics following multiple administrations.
Number of Subjects	18
Main Inclusion Criteria	Males and females between the ages of 18-65 years
Study Product, Dose, Route, Regimen	Narcan (naloxone hydrochloride) intranasal spray, 4 mg/nostril repeated 4 times within 8 hours alternating nostrils.
Duration of Administration	4 doses of 4 mg or 2 doses of 8 mg administered over 1 day.
Endpoints	Primary endpoint will be the within person difference in peak epinephrine secretion during the morning episodes of hypoglycemia on days one and two; we will compare this difference between the two treatment conditions.
	Secondary endpoint will be naloxone pharmacokinetics including maximum concentration (Cmax), time to maximum concentration (Tmax) and area under the curve (AUC).
Statistical Methods	We will fit a general linear mixed model with fixed effects for treatment (naloxone vs. placebo), treatment order (naloxone first vs. placebo first), and period (Part 1 vs. Part 2) and a random effect for participant. We will also consider adjustment for important baseline characteristics, such as age and sex. Diagnostics will be examined to assess model assumptions.

List of Abbreviations

AE	Adverse Event	
CFR	Code of Federal Regulations	
CRF	Case Report Form	
DSMB	Data and Safety Monitoring Board	
DSMP	Data and Safety Monitoring Plan	
FDA	Food and Drug Administration	

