4.0 Study Objectives

4.1 **Primary Objective**

Primary endpoint will be the within person difference in peak epinephrine secretion during the morning episodes of hypoglycemia on days one and two; we will compare this difference between under the two treatment conditions (parts 1 and 2). Epinephrine secretion during hypoglycemia is assessed by collecting blood samples for measurement of epinephrine concentrations at baseline and every 15 minutes during the period of hypoglycemia (starting at point where blood glucose is first < 55 mg/dl) in the clamp studies done in the mornings of days 1 and 2 of both parts 1 and 2.

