5.0 Study Design

5.1 Overview of Study Design

This is a single center, single-blind randomized cross over design trial that will compare the impact of intra-nasal naloxone vs. intra-nasal placebo administration during experimental hypoglycemia on day one vs. day two. We intend to enroll 18 individuals to obtain the complete data sets from 15 participants. Initially up to 8 of these subjects will receive intra-nasal naloxone first prior to placebo in order to evaluate tolerability and to ensure that the desired drug concentrations are achieved. Double-blinding is not possible because we will not be able to replicate for the placebo (placebo) the same delivery device as is being provided by the manufacturer for the naloxone; the manufacturer is unable to provide placebo-charged devices for us to use as placebo. Our own labeling will be put over both naloxone and placebo devices in order to obscure any device labeling that would break the blind for the participant. Expected duration of subject participation is 10-12 weeks. This study will consist of two 2-day intervention visits separated by approximately 8 weeks.

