7.2 Statistical Methods

Our primary outcome is the peak epinephrine response during the third hypoglycemic clamp of each infusion experiment, thus each participant will have two observations: one from their naloxone experiment and one from their placebo experiment. We will fit a general linear mixed model with fixed effects for treatment (Naloxone vs. placebo), treatment order (Naloxone first vs. placebo first), and period (Part 1 vs. Part 2) and a random effect for participant. We are confident that our study design, with a washout period of 8 weeks between Parts 1 and 2, has minimized the possibility of a treatment effect from Part 1 that lingers into Part 2. We will also consider adjustment for important baseline characteristics, such as age and sex. Diagnostics will be examined to assess model assumptions.

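### The primary endpoint is defined in two incompatible ways (day 1/day 2 difference, or day 2 clamp alone), and the 85% power is not established for the day difference

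*Combined protocol and SAP*

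**What the plan says.** Four places give the primary endpoint as a difference between days. Section 5.3.1 says: "Primary endpoint will be the within person difference in peak epinephrine secretion during the morning episodes of hypoglycemia on days one and two". The Study Summary and the opening of 5.4.1 say the same. Section 4.1 adds that epinephrine is sampled "in the clamp studies done in the mornings of days 1 and 2 of both parts 1 and 2", so this definition uses four morning clamps per person.

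Section 7.2, the only section that describes the efficacy analysis, says: "Our primary outcome is the peak epinephrine response during the third hypoglycemic clamp of each infusion experiment". In the schedule of 6.4.1 the third clamp is the single clamp on day 2, so this definition uses two clamps per person. The mixed model has fixed effects for treatment, treatment order and period, and a random participant effect.

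Section 5.4.1 opens with the day difference, then reasons from the third clamp and counts one response per treatment. It sizes the trial on 157 pg/ml, a paired-difference SD of at most 216 pg/ml, 15 completers, one-sided 5% and 85% power. The 157 is the gap between 278 ± 134 pg/ml in controls and 121 ± 168 pg/ml in people with type 1 diabetes in an earlier study, where response meant hypoglycemia against euglycemia.

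Under 6.4.1, naloxone or placebo is given after the baseline samples and before the day 1 morning clamp starts. No day 2 dose is described.

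**The concern.** The day 1 clamp is not an untreated reference. If naloxone acutely raises epinephrine on day 1, the day difference subtracts that rise from the protection seen on day 2 and understates prevention. Section 2.0 makes such a rise plausible: it reports that intravenous naloxone given during hypoglycemia increased the counterregulatory response. It does not name epinephrine or give a size.

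The primary result therefore depends on which section the analyst follows. The trial is single-blind (5.1: "Double-blinding is not possible because we will not be able to replicate" the device), so the choice could be made with knowledge of treatment and data. The power statement also cannot simply be carried over to the endpoint named in four places.

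Three smaller gaps go with this:

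- **Response is not fixed.** Sections 4.1 and 5.3.1 plan a baseline sample but do not say whether it is subtracted from the peak.
- **The expected pattern is confused.** Section 5.4.1 predicts a large positive placebo third-clamp response if naloxone works. That does not fit a benefit on the 7.2 endpoint; it may be a slip or a remnant of a change score.
- **The test is not carried through.** The one-sided 5% level of 5.4.1 does not appear in 7.2.

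**Working it through.** **1. What each definition estimates.** Let N1, N2, P1, P2 be mean peak epinephrine under naloxone and placebo on days 1 and 2. Let A = N1 − P1 (acute effect) and B = N2 − P2 (day 2 protection).

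- Section 7.2: N2 − P2 = B.
- Day difference, as day 2 minus day 1: (N2 − N1) − (P2 − P1) = B − A. Reversing the days changes only the sign.

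They agree only if A = 0.

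**2. The plan's own figure.** Paired t, n = 15, 14 df, one-sided 5%: noncentrality = (157/216) × √15 = 2.815, critical value 1.761, power **84.9%**. The stated 85% reproduces. All eight cells of the 5.4.1 table reproduce as SD × √(2(1 − ρ)), for example 170 × √1.6 = 215. That is the SD of a difference between two single responses.

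**3. The day difference.** Assume one SD for all four clamps, within-Part correlation rw, and one common correlation rb for every pair of clamps from different Parts. Then

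- 7.2 endpoint: SD × √(2(1 − rb));
- day difference: 2 × SD × √(1 − rw).

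Power with B = 157, A = 0, n = 15 and rb = 0.2 (correlations assumed; SDs from the 5.4.1 table):

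| Response SD | 7.2 endpoint | Day diff., rw = 0.2 | rw = 0.6 | rw = 0.7 |
|---|---|---|---|---|
| 170 | 85% (SD 215) | 60% (SD 304) | 85% (SD 215) | 93% (SD 186) |
| 135 | 96% (SD 171) | 77% (SD 241) | 96% (SD 171) | 99% (SD 148) |

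The two SDs are equal when rw = (1 + rb)/2. The day difference stays within the protocol's 216 limit when rw ≥ 1 − (216/(2 × SD))², which is 0.60 at SD 170 and 0.36 at SD 135.

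**4. Adding an acute effect.** The mean contrast becomes 157 − A. At SD 170, rw = 0.7, rb = 0.2 (paired SD 186.2), with A assumed:

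- A = 0: 93%
- A = 25: 83%
- A = 50: 68%
- A = 157 × (1 − 186.2/215.0) ≈ 21: 85%, level with 7.2

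**5. How well A could be estimated.** The planned day 1 samples under both treatments give N1 − P1. If that paired difference has an SD in the range of the 5.4.1 table (85 to 215), the 95% confidence interval half-width is 2.145 × SD/√15, or **47 to 119 pg/ml**.

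**6. Effect of the period term.** The 85% ignores the period adjustment in 7.2. With it, SE = (216/2) × √(1/n1 + 1/n2) on 13 df. Section 5.1 says: "Initially up to 8 of these subjects will receive intra-nasal naloxone first prior to placebo". If the other 7 of 15 completers split 3:4 or 4:3, the sequences are 11:4 or 12:3 (assumed).

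| Split | SE | Power for 157 |
|---|---|---|
| 8:7 | 55.9 | 84.5% |
| 11:4 | 63.1 | 76% |
| 12:3 | 69.7 | 69% |

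This applies to either endpoint and does not favour one over the other.

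**The case against.** The strongest reply is that the contradiction is real but the choice belongs to the sponsor, and the day difference has a good claim. It is stated in four places, matches the day one versus day two comparison in 5.1, and is closest to the blunting aim in 7.1. The 7.2 model takes one value per treatment, so a change score fits it once one sentence is replaced. The day difference can also be the more precise endpoint (93% against 85% above). This stands: the plan must choose and justify, and day 2 is a recommendation.

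The sizing inputs are also borrowed for both endpoints. They come from a between-group comparison of patients and controls, and nothing says they are third-clamp data in healthy volunteers. They match 7.2 in form (one response per treatment), which is weaker support than a direct match.

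The size of A is unknown, and the day 1 contrast would estimate it poorly: a half-width of 47 to 119 pg/ml cannot exclude the roughly 21 pg/ml that cancels the precision gain in step 4. That is correct. It also means the trial could not reliably correct a day-difference result for A afterwards.

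Finally, the equal cross-Part correlation is restrictive. In general the day-difference SD is 2 × SD × √(1 + rc − rs − rw), with rs the same-day and rc the cross-day correlation between Parts. With SD 170, rw = 0.5, rs = 0.3 and rc = 0.2 (assumed), it is 215 and power is 85%. So the 0.60 threshold and the (1 + rb)/2 rule are not general. None of these points removes the contradiction or supplies the missing SD and effect.

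**Conclusion.** The concern holds and must be fixed. The plan has two primary endpoints and one power calculation. One endpoint tests B, the other B − A, and nothing elsewhere in the documents says which governs.

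The 85% is arithmetically right for a single response per treatment in an unadjusted paired t test. It is not established for the day difference: under the assumptions in step 3, power with no acute effect runs from 60% to 99%, and any positive acute effect lowers it. This does not show that the trial is underpowered. The existence of the contradiction rests on no assumption; the power range rests on assumed correlations, assumed values of A and, for step 6, assumed sequence splits.

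**What to change.** - State one primary endpoint in identical words in the Study Summary, 4.1, 5.3.1, 5.4.1 and 7.2. The day 2 (third clamp) response is recommended: it separates prevention from an acute day 1 effect, and it is the form that 7.2 and the sizing already use.
- Define response, including whether the planned day 2 baseline is subtracted.
- Report the day 1/day 2 difference as secondary, together with the day 1 naloxone minus placebo contrast and its confidence interval.
- If the day difference stays primary, align 7.2 with it, justify the on-treatment day 1 reference, and restate power using an SD and expected effect for the change.
- In either case, correct the 5.4.1 sentence on the placebo third-clamp response, carry the one-sided 5% test and its direction into 7.2, and either label the 85% as an unadjusted paired t figure or restate it for the 7.2 model.

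**Cost.** Under 6.8 this is a protocol amendment with investigator agreement and IRB approval. It needs no new samples or subjects. Because the trial is single-blind, the amendment should record that the choice was made without reference to results; this limits the integrity concern but does not fully remove it. Choosing day 2 demotes the definition given in four places and closest to the aim in 7.1.

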5.3.2 Secondary Clinical Endpoint

To characterize the pharmacokinetic parameters of intranasal naloxone which will include C_{max} (ng/ml), T_{max} (minutes), half-life (hours), AUC (0-> infinity), clearances (CL), and volume of distributions (V). Please refer to Section 6.4.3 for parameter definitions.

5.4 Study Population

18 subjects 18-65 years of age will be enrolled in the study. The investigators will recruit and screen subjects.

5.4.1 Sample Size

We plan to enroll 18 subjects.

We propose a two-period two-treatment cross-over study, where each participant gets intra-nasal naloxone and intra-nasal placebo, in randomized order. Primary endpoint will be the within person difference in peak epinephrine secretion during the morning episodes of hypoglycemia on days one and two; we will compare this difference between under the two treatment conditions. Thus each participant will have two observations: one epinephrine response from their naloxone experiment and one epinephrine response from their placebo experiment. We expect to recruit 18 individuals in order to complete 15 studies. Additional participants will be recruited if needed to have 15 completed studies. If naloxone prevents IAH, then the epinephrine response during the third hypoglycemic clamp after naloxone infusion will still be high, while the epinephrine response during the third hypoglycemic camp after placebo infusion will be large and positive. If naloxone does not prevent IAH, then this within-person difference will be close to zero.

In a previous study between healthy controls and subjects with T1D and impaired awareness of hypoglycemia, participants underwent a hyperinsulinemic hypoglycemic clamp (the same clamp procedure as proposed here) and the epinephrine response (the difference in peak epinephrine between euglycemia and hypoglycemia) was 121 ± 168 pg/ml in the subjects with T1D vs. 278 ± 134 pg/ml

in controls. We have powered this study to achieve a similar magnitude of difference between naloxone and placebo (a paired comparison) as was seen previously between controls and diabetics (a two-sample comparison). Assuming 15 completers, a one-sided type I error of 5%, and a power of 85%, a paired difference between naloxone epinephrine response and placebo epinephrine response of at least 157 pg/ml is statistically detectable if the between-person standard deviation of the paired naloxone vs. placebo difference is *no more than* **216** pg/ml.

This standard deviation of the paired difference is a function of the standard deviation of the epinephrine response and the within-person correlation between the two epinephrine responses (one after naloxone, one after placebo). As can be seen from the Table below, we are conservatively powered, as our preliminary data suggest that our observed standard deviation will be smaller than 216 pg/ml.

Table. Estimated standard deviation (SD) of the paired difference between naloxone epinephrine response and placebo epinephrine response when the within-person correlation is ρ

	$\rho = 0.2$	ρ = 0.4	ρ = 0.6	$\rho = 0.8$
SD in epi response = 135	171	148	121	85
SD in epi response = 170	215	186	152	108

5.4.2 Subject Recruitment

Healthy participants will be recruited from IRB-approved public notices. [name], [name] or [name] will make initial contact with subjects potentially interested and will discuss the investigation and conduct the informed consent discussion at least 24 hours before study medication is to be given.

5.4.3 Subject Screening

Drs. [name] or [name] will complete a phone screen with each participant. Subjects will sign the consent form on the study visit, and will have a medical history and current medications recorded. A routine physical, and pregnancy test (if relevant), will be completed on the study visit.

5.4.4 Prior and Concomitant Therapy

Neither prescribed, other than hormonal birth control, nor over-the counter medications will be allowed for 48 hours (two days) prior to, nor for 24 hours after, receiving naloxone.

5.4.5 Inclusion Criteria

Subjects will be eligible to participate in the study if all of the following conditions exist:

- 1. Males and females between the ages of 18-65 years.
- 2. Subjects are capable of giving informed consent.
- 3. Female subjects must be post-menopausal for at least 1 year, or surgically incapable of bearing children, or practicing at least one or more of the following methods of contraception for three months prior to, and during the study: hormonal, intrauterine device (IUD), or barrier method in combination with a spermicide.
- 4. Subject should be medication free, other than hormonal birth control, for 48 hours before through 24 hours after study drug administration. If the need for medication is identified during this time period, it will be discussed with and approved by the PI.

5.4.6 Exclusion Criteria

Subjects will be excluded from participation in the study if any of the following conditions exist:

- 1. Women who are pregnant.
- 2. Women who are breastfeeding.
- 3. Subject has a known hypersensitivity to naloxone.
- 4. Subject with hypertension
- 5. Subject has a significant history of cardiac, neurologic, psychiatric, oncologic, endocrine (including diabetes type I or type II), metabolic, renal or hepatic disease
- 6. Subject has taken or used any investigational drug or device in the 30 days prior to screening.
- 7. Subject has taken either prescribed or over the counter medication for 48 hours prior to study drug administration on either of the study days, other than hormonal birth control.
- 8. History of narcotic or heroin abuse.

5.4.7 Exit/Discontinuation Criteria

Subjects will exit the study if any of the following conditions exist:

- 1. Subject voluntarily withdraws from the study.
- 2. Subject death.
- 3. Subject acquires any of the listed exclusion criteria.
- 4. Subject completes the protocol.
- 5. Subject is non-compliant with the protocol (See Section 6.7 for definition of non-compliance)

- 6. Subject's well-being, in the opinion of the Investigator, would be compromised by study continuation.
- 7. Subject experiences concurrent illness.
- 8. Subject experiences a serious adverse event.
- 9. IRB recommendation

Even if subjects who received study drug exit the study, they will be followed for 24 hours to ascertain if any Adverse Event occurs.

6.0 Study Procedures

6.1 Informed Consent

All subjects for this study will be provided a consent form describing this study and providing sufficient information for subjects to make an informed decision about their participation in this study. The consent form will be submitted with the protocol for review and approval by the IRB for the study. The formal consent of a subject, using the IRB-approved consent form, must be obtained before that subject participates in any study procedure. This consent form must be signed by the subject, and the investigator-designated research professional obtaining the consent. A blank copy of the IRB-approved form must be kept on-site and by the sponsor-investigator.

6.2 Randomization Scheme

The investigational pharmacy at the University of Minnesota will be responsible for implementing the randomization order in which participants are given naloxone or placebo, prepared by the study statistician.

6.3 Laboratory Testing Procedures

6.3.1 Frequency of Blood Draws

Three to five milliliter blood samples will be collected for determination of plasma naloxone concentrations prior to dosing, at 5 ± 1 , 15 ± 2 , 30 ± 3 minutes, and at 1.08 ± 5 , 1.5 ± 5 , 2, 3, 4, and 6 hours after completion of the first IN dose. The actual blood collection times for hours 2 through 6 may deviate by ± 10 minutes from the specified times. In all cases, the actual time of the blood draw will be recorded. Missed samples or breakage of a sample will be recorded.

Baseline blood samples will be drawn for glucose, glucagon, epinephrine, norepinephrine and cortisol before the dose of Naloxone or placebo and before the start of the insulin clamp. During the morning study on day 1, blood samples will be collected every 5 minutes for monitoring of blood glucose levels and every 15 minutes during the last 90 minutes of the clamp, for later measurement of serum glucagon, epinephrine, norepinephrine and cortisol. Afternoon clamp on day 1 will proceed as in the morning except that no serum or plasma will be collected except

for the monitoring of glucose and collection of samples for subsequent measurement of naloxone. On day 2 blood samples will be collected as on the morning of day 1.

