6.4 Clinical Procedures

6.4.1 Treatment Regimen

This study will consist of two 2-day intervention visits separated by approximately 8 weeks.

Subjects will be asked to report to the research center by 7 am on the first day of the study after fasting overnight. On arrival, intravenous lines will be placed in each arm (one will be used for infusions and the other for blood sampling). A minimum of 30 minutes after the IVs are placed, baseline blood samples will be drawn for later measurement of glucose, glucagon, epinephrine, norepinephrine, and cortisol. Subjects will then be given a 4 mg (0.1 ml) or 8 mg dose (0.2 mL of IN naloxone or a similar volume of IN placebo.. After naloxone or placebo dose, a hyperinsulinemic (2.0 mu/kg/min) hypoglycemic (target = 50 mg/dl) clamp protocol will be started. The clamp will be maintained for 2 hours. Blood samples will be collected every 5 minutes for monitoring of blood glucose levels and every 15 minutes during the last 90 minutes for later measurement of serum glucagon, epinephrine, norepinephrine and cortisol. If the subject received 4mg dose of IN naloxone or placebo, a second dose of 4 mg IN naloxone or placebo will be given at +30 min after the start of insulin clamp. Every 15 minutes during the last 90 minutes minutes of the morning clamp, subjects will be asked to quantitate their hypoglycemia related symptoms using a standardized questionnaire (12). At the completion of the morning clamp, glucose will be given to return the participant to normal glucose. 2 hours after the end of the morning clamp, a second 2 hour hyperinsulinemic (2.0 mu/kg/min) hypoglycemic (target = 50 mg/dl) clamp protocol will be started. At the start of this afternoon clamp study, a dose of 4 mg or 8 mg of IN naloxone or placebo will be given. Afternoon clamp will proceed as in the morning except that no serum or plasma will be collected except for the monitoring of glucose and collection of samples for subsequent measurement of naloxone. If the subject received 4 mg dose of intra-nasal naloxone or placebo, a second dose of 4 mg intra-nasal naloxone or placebo will be given after 30 minutes. After the completion of the afternoon clamp, subjects will be returned to euglycemia and fed a meal. They will then be allowed to leave the research center with instructions to return the next morning after an overnight fast. At 7 AM on day 2 they will undergo a single 2 hour hyperinsulinemic hypoglycemic clamp (target blood glucose 50 mg/dl) during which blood samples will be collected as on the morning of day 1. Symptom scores will be collected every 15 minutes during the last 90 minutes of the clamp. At the end of the study, infusions will be stopped, and participants will be fed a meal and then sent home after they are scheduled to return for Part 2 in 8 weeks. This timing is selected to ensure that female participants are studied at the same phase of the menstrual cycle; males will return for Part 2 in 8 ± 2 weeks. During Part 2 they will receive the treatment not provided during Part 1. The rest of the study protocol will be the same as in Part 1.

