6.4.3 Drug Assay and Pharmacokinetic Analyses

A validated, liquid chromatography-mass spectroscopy assay will be used to measure naloxone concentrations.

Non-compartmental Pharmacokinetics Analysis: T_{max} and C_{max} will be determined from visual inspection of the naloxone concentration-time plots. Pharmacokinetic analysis will be performed with WinNonLin (Certara, Princeton, NJ, USA), a pharmacokinetic data

analysis package, and will include calculation of the area under the concentration-time curve (AUC) as well as other parameters as detailed below. Descriptive statistics will be used to summarize the data from this study. Descriptive statistics will include numbers of subjects (n), mean, median, standard deviation (SD), minimum, and maximum for continuous data and frequencies and percentages for categorical data. For each subject, the following pharmacokinetic parameters will be determined:

- C_{max}: maximum observed plasma concentration
- T_{max}: time to C_{max}
- AUC_{0-t}: area under the plasma concentration-versus-time curve from time zero to the last sampling time at which concentrations were at or above the limit of quantification, calculated by the linear trapezoidal rule
- AUC_{0-12hr}: area under the plasma concentration-versus-time curve from time zero to 12 hours post-dose
- AUC_{0- ∞}; area under the plasma concentration-versus-time curve from time zero to infinity, calculated from AUC_{0-t} + (Ct/ λz), where Ct is the last observed quantifiable concentration
- λz : apparent terminal rate constant λz obtained from the slope of the line, fitted by linear least squares regression, through the terminal points of the natural log of the concentration-versus-time plot of these points
- $t_{1/2}$: apparent terminal half-life, calculated from $(\log_e 2)/\lambda z$
- CL: clearance
- V_d: volume of distribution

Plasma naloxone concentrations below the limit of quantification (BLQ) of the assay will be taken as zero for all calculations. All calculations will be made using raw data.

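### AUC from 0 to 12 h extends past any planned naloxone sample, and on the listed times the terminal-slope rule crosses a new dose

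*Combined protocol and SAP*

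**What the plan says.** - **Sampling.** Section 6.3.1 lists a pre-dose sample, early samples from 5 min onward, and then draws at "2, 3, 4, and 6 hours after completion of the first IN dose". It adds: "The actual blood collection times for hours 2 through 6 may deviate by ± 10 minutes from the specified times".
- **Afternoon samples.** Sections 6.3.1 and 6.4.1 say the afternoon clamp follows the morning pattern, with no blood kept "except for the monitoring of glucose and collection of samples for subsequent measurement of naloxone". No times are given.
- **Day 2.** Section 6.3.1: "On day 2 blood samples will be collected as on the morning of day 1". It does not say whether this includes naloxone.
- **Dosing.** The Section 6.4.1 text has a 2 h morning clamp, a 2 h gap and then a second clamp: "At the start of this afternoon clamp study, a dose of 4 mg or 8 mg of IN naloxone or placebo will be given". In the 4 mg regimen another spray follows 30 min later. The visit table puts the clamps at 8 AM and 1 PM and shows a single afternoon 4 mg dose. Section 2.0 places a third dose about 4 h after the second.
- **Analysis.** Section 6.4.3 lists AUC0-12hr, the "area under the plasma concentration-versus-time curve from time zero to 12 hours post-dose", without saying which dose. The terminal rate constant is a slope "fitted by linear least squares regression, through the terminal points of the natural log of the concentration-versus-time plot", with no rule for choosing the points. AUC0-infinity and half-life are built on it. AUC0-t is also listed, and compartmental and NONMEM modelling is planned in addition.
- **Endpoints.** Section 5.3.2 names Cmax, Tmax, half-life, AUC0-infinity, CL and V, and refers to Section 6.4.3 for definitions. AUC0-12hr is not among them.

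**The concern.** Naloxone pharmacokinetics after repeated doses is the only secondary objective (Section 4.2). One listed parameter needs concentrations to 12 h, and no written provision reaches that far. The slope rule suits a single dose followed by uninterrupted decline. Here dosing resumes inside the listed sampling window, so the last listed points lie on both sides of a new dose. Whoever runs the non-compartmental analysis must choose the points after seeing the data, and half-life, AUC0-infinity, CL and V all follow from that choice.

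**Working it through.** The plan gives no figure of its own to reproduce here, so the check is a timeline and a model.

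**1. Timeline, first dose at clamp start.** The afternoon dose falls at 2 + 2 = 4 h (Section 6.4.1 text) or 13:00 − 8:00 = 5 h (visit table). The last dose is at 4 to 5.5 h, depending on regimen. The only later listed draw is at 6 h, 0.5 to 2 h after the last dose. If the first dose precedes the clamp by 30 min, with four sprays and a 1 PM clamp, the last dose is at 0.5 + 5 + 0.5 = 6 h and no listed draw follows it.

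**2. Latest possible data on day 1.** The stay of 3 h after the last dose (Section 6.7) ends at 7 to 8.5 h, or 9 h with the 30 min lead. A day 2 naloxone draw at about 24 h would be 18.5 to 20 h after the last dose. That is 18.5/2.1 = 8.8 to 20/2.1 = 9.5 half-lives, and it leaves the gap unfilled.

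**3. Model.** One compartment with first-order absorption; half-life 2.1 h (Section 2.0), so k = 0.693/2.1 = 0.330 per h. The absorption rate ka is assumed to be 2, 4, 6 or 10 per h. For a dose D, with s hours since that dose and unit volume:

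- C = D·ka/(ka−k)·(e^(−ks) − e^(−ka·s))
- AUC to s = D·ka/(ka−k)·[(1−e^(−ks))/k − (1−e^(−ka·s))/ka]

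Doses are summed. AUC0-12h is counted from the first dose, the reading kindest to the plan.

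**4. Example: 8 mg at 0 and 4 h, ka = 6.** ka/(ka−k) = 1.058. Per mg of each dose:

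- AUC to 6 h = 2.587 + 1.373 = 3.960
- AUC to 7 h (end of stay) = 2.712 + 1.839 = 4.550
- AUC to 12 h = 2.969 + 2.801 = 5.770

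Share after 6 h: 1 − 3.960/5.770 = 31.4%. Share after 7 h: 1 − 4.550/5.770 = 21.1%.

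**5. All schedules, ka 2 to 10.**

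| Doses (h) | AUC0-12h after 6 h | AUC0-12h after end of stay |
|---|---|---|
| 4 mg at 0, 0.5, 4, 4.5 | 33.5–38.8% | 18.3–21.4% |
| 8 mg at 0, 4 | 30.6–35.5% | 20.6–24.1% |
| 4 mg at 0, 0.5, 4 | 25.3–29.3% | 17.0–19.8% |
| 4 mg at 0, 0.5, 5 | 31.8–36.2% | 14.0–16.3% |
| 4 mg at 0, 1, 5 | 32.8–37.4% | 14.4–16.8% |
| 4 mg at 0, 0.5, 5, 5.5 | 44.6–49.5% | 15.5–18.2% |
| 8 mg at 0, 5 | 40.7–46.2% | 17.9–20.9% |

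Overall this is about 25 to 50% after 6 h and about 14 to 24% after the stay. With the 30 min lead, the share after 6 h reaches up to 55% (at ka 1.5).

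**6. Slope, same example.** Concentrations at 2, 3, 4 and 6 h are 4.375, 3.145, 2.261 and 5.543 (logs 1.476, 1.146, 0.816, 1.713).

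- 3/4/6 h fit: slope = 1.055/4.667 = +0.23 per h. It rises, so there is no half-life. The same sign appears in all seven schedules at every ka.
- 2/3/4 h fit: slope = (0.816 − 1.476)/2 = −0.330 per h, half-life 2.1 h. Across the schedules the half-life is 2.1 to 2.6 h. This is an inter-dose slope.
- 4 h draw taken 10 min late with the afternoon dose at exactly 4 h: the concentration is 8.466 × (0.253 + 0.946 − 0.368) = 7.04, above the 3 h value. The 2/3/4 h fit is then spoiled too.

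**The case against.** The strongest reply is that the afternoon clamp is described as following the morning one, with naloxone samples kept. If the morning draw times repeat after the afternoon dose, within the 3 h stay, the last three points give a half-life of 2.1 to 2.7 h and AUC0-infinity of 97 to 107% of true under the same model. That stands: the slope problem is then largely a matter of unwritten times. It does not help AUC0-12h, because the stay still ends before 12 h.

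Second, the compartmental and population models handle repeated doses, and actual draw and dose times are recorded (Sections 6.3.1 and 9.3). AUC0-t already covers AUC to the last quantifiable sample. This also stands. But the models are an additional analysis, Section 6.4.3 defines half-life and AUC0-infinity by the slope, and the plan does not say which result is reported.

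Third, a rising 3/4/6 h slope would be rejected on sight, and the obvious substitute, 2/3/4 h, errs little. That is true if the 4 h draw precedes the dose, which the ±10 min window does not ensure when dosing resumes at 4 h.

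A reader might infer more than this:

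- **That the half-life could be badly wrong.** With a late 4 h draw the 2/3/4 h fit gives 5.0, 12.6 or 83 h in three of eight scenarios and a rising slope in five. Those figures need the afternoon dose exactly 4 h after the first. Section 6.4.1 gives the first dose before the clamp starts, so 4 h is the minimum interval; with a 30 min lead, a draw at 4 h 10 min still precedes the dose.
- **That no samples are planned after the last dose, or that the pharmacokinetic objective is lost.** The documents foresee afternoon samples and a model that can use them.

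**Conclusion.** The point holds in limited form. AUC0-12h cannot be observed under any reading of the plan: about 25 to 50% of it lies beyond the last listed draw, and about 14 to 24% beyond the required stay. These shares rest on one compartment, a 2.1 h half-life, an assumed ka of 2 to 10 per h and the first dose at clamp start.

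The slope rule fails as written on the listed times, but this can be repaired by choosing an interval between doses, or may already be resolved if the morning draws were meant to repeat. The secondary objective is impaired, not lost: the planned model can still estimate the named endpoints. The primary epinephrine endpoint is not touched. This should be corrected, but it does not threaten the trial.

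**What to change.** 1. Delete AUC0-12h from Section 6.4.3 and keep AUC0-t to the last quantifiable sample.
2. Name the compartmental/NONMEM model, with actual dose and draw times, as the source of half-life, AUC0-infinity, CL and V.
3. State that no non-compartmental slope is fitted across a dose. Use only samples between the last morning dose and the afternoon dose, with the 4 h draw taken before that dose, or only samples after the last dose.
4. Write down the afternoon naloxone times that Sections 6.3.1 and 6.4.1 already imply, with at least three after the last dose and within the 3 h stay. Before that, the sponsor must reconcile the Study Summary, Section 2.0, the Section 6.4.1 text and the visit table on the number and timing of doses.

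As a check, a draw just before the afternoon dose plus draws at 1, 2 and 3 h after the last dose gives a half-life of 2.1 to 2.8 h and AUC0-infinity of 92 to 106% of true under the same model.

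Cost: items 1 to 3 change wording and fix the order of one draw. If the afternoon draws were not already intended, item 4 adds about three draws of 3 to 5 mL (9 to 15 mL) per day 1 visit. The changes go through an IRB-approved amendment (Section 6.8). Further early afternoon draws to capture Cmax are optional and not part of this correction.
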